5.7.6 Classification of Seizures from EEG

Table 3 shows the seizure classifications that are distinguished in the EEG and which are counted when deriving absence seizures endpoints.

Table 3: Seizure Classification by EEG

Label	Definition	Absence Seizure
GenTC-BMS	Generalized Tonic-Clonic	
GenT-BMS	Generalized Tonic	
GenC-BMS	Generalized Clonic	
Partial-BMS	Partial	
AbsenceAwake-BMS	Absence Awake (≥ 10 sec)	X
AbsenceSleep-BMS	Absence Sleep (≥ 10 sec)	X
IndetAbsenceAwake-BMS	Indeterminate Absence Awake (3-10sec)	X
IndetAbsenceSleep-BMS	Indeterminate Absence Sleep (3-10sec)	X
Myoclonus-BMS	Myoclonus	

5.8 Other Derived Efficacy Variables

5.8.1 Cambridge Neuropsychological Test Automated Battery (CANTAB)

The CANTAB scores are shown in Table 4. The Motor Screening Test (MOT) is only used to evaluate whether the subject is eligible to continue with the remaining tests.

Table 4: CANTAB Scores

Cognitive Domain	Specification	Sense	Form	Range
Attention	RTI Simple choice reaction time standard deviation (RTISRTSD)	Lower is better	Continuous	0-5000
Reaction Time	RTI median simple choice reaction time (RTIMDSRT)	Lower is better	Continuous	100-5100 (ms)
Reaction Time	RTI median 5-choice reaction time (RTIMDFRT)	Lower is better	Continuous	100-5100 (ms)
Episodic memory/ new learning	PAL total errors adjusted (PALTEA)	Lower is better	Discrete ordinal	0-137
Episodic memory	PAL first trial memory score (PALFTMS)	Higher is better	Discrete ordinal	0-27
Sequential memory	SSP Span Length (SSPSLF)	Higher is better	Discrete ordinal	2-9
Working Memory	SWM between errors (SWMBE48)	Lower is better	Discrete ordinal	0-360
Executive function/ strategy	SWM strategy (SWMS68)	Lower is better	Discrete ordinal	4-28

5.8.2 Percent predicted 6MWT distance

The percent predicted 6MWT formula which is applicable at enrollment will be used for that subject throughout the study.

To calculate the percent predicted 6MWT value, the following formulas will be applied for subjects aged < 20 years old ([Geiger et al. 2007](#)).

For males:

$$X_i = \frac{X_{0i}}{196.72 + (39.81 * Age) - (1.36 * Age^2) + (132.28 * Height)} * 100$$

and for females:

$$X_i = \frac{X_{0i}}{188.61 + (51.50 * Age) - (1.86 * Age^2) + (86.10 * Height)} * 100$$

where X_i is the percent predicted 6MWT result at time i for subject X , and X_{0i} is the 6MWT result (in meters) at time i for subject X . Height and age at the study visit will be used for the calculation for the duration of the study. If height is missing at the study visit then the nearest available measurement will be used. If there are no height measurements then percent predicted will not be calculated.

To calculate the percent predicted 6MWT value, the following formula will be applied for subjects aged ≥ 20 years old ([Gibbons et al. 2001](#)).

$$X_i = \frac{X_{0i}}{868.8 - (2.99 \times Age) - (74.7 \times Gender)} * 100$$

where X_i is the percent predicted 6MWT result at time i for subject X , X_{0i} is the 6MWT result (in meters) at time i for subject X , and $Gender$ is equal to 0 if the subject is male or 1 if the subject is female. Height at baseline will be used for calculation for the duration of the study, and age at the study visit will be used for the calculation for the duration of the study. If height is missing then the nearest available measurement will be used.

5.8.3 Gross Motor Function Measure-88 (GMFM-88)

The GMFM-88 scores include the following:

- Lying & Rolling Score, Range 0–100%, Higher is better
- Sitting Score, Range 0–100%, Higher is better
- Crawling & Kneeling Score, Range 0–100%, Higher is better
- Standing Score, Range 0–100%, Higher is better
- Walking, Running & Jumping Score, Range 0–100%, Higher is better
- Total Score = (Sum of 5 Above Scores) / 5, Range 0–100%, Higher is better

5.8.4 Columbia Neurological Score (CNS) total score

The CNS is a quantitative tool developed to summarize neurological exam findings ([Kaufmann et al. 2004](#)). The Columbia Neurologic Score (CNS) is the sum of scores for the following domains: Weight (max=1), Height (max=1), Head Circumference (max=1), General Medical Exam (max=13), Funduscopic Exam (max=4), Cranial Nerves (max=12), Stance & Gait (max=7), Involuntary Movements (max=7), Sensation (max=3), Cerebellar Function (max=8), Muscle Bulk, Tone & Strength (max=6), Myotatic Reflexes (max=10), Toe Sign (max=2), Other Findings (max=1). The CNS is only scored when all domains are measured and ranges from 0 (abnormal exam) to 76 (normal exam). Higher scores are associated with higher neurological function.

5.8.5 Peabody Picture Vocabulary Test (PPVT) standardized score

The PPVT is a test of receptive vocabulary achievement and verbal ability that is normed for children as young as 2 years of age ([Dunn et al. 2007](#)). The PPVT results in the following scores:

- Raw Score [PPVTRAW], Range 0–228, higher is better

- Standard Score [PPVSTSCR], Range 20–160, higher is better
- 95% Confidence Interval-Upper [PPVCONUP], Range 20–166, higher is better
- 95% Confidence Interval-Lower [PPVCONLO], Range 14–154, higher is better
- Percentile Rank [PPVTPERC], Range <0.1 – >99.9, higher is better
- Age Equivalent [PPVTAGEQ], Range <2:0 – >24:11, higher is better
- Growth Scale Value (GSV) [PPVTGSV], Range 12–271, higher is better

5.8.6 SF-10 Health Survey

The SF-10 Health Survey is assessed for children 5 to 17 years of age. Two summary measures (the Physical Summary Score and the Psychosocial Summary Score) are calculated from raw scores to have a mean of 50 and SD of 10.

The T-score Based scoring (described in Section 5.8.7) is also used to score the SF-10 Health Survey for Children summary scales. The scale scores have been centered so that a score of 50 corresponds to the average score in a comprehensive 2006 sample (a combination of general population and supplemental disability and chronic condition samples). Although scale scores are standardized to a mean of 50 and a standard deviation of 10 in the combined U.S. general population and clinical samples, age-specific t-scoreative data should always be used for comparison purposes when results for individual children are being considered or when aggregate data are limited to a specific age range for which t scoreative data are available.

5.8.7 SF-12 Health Survey version 2

The SF-12 Health Survey version 2 is assessed for adults 18 years of age and older. Eight domain scores (Physical Functioning, Role Limitations due to Physical Health, Bodily Pain, General Health Perceptions, Vitality, Social Functioning, Role Limitations due to Emotions Problems, and Mental Health) are calculated from raw scores. Additionally two summary component scores are calculated from domain scores (Physical Component Summary Scale [PCS] and the Mental Component Summary Scale [MCS]).

Raw scores range from 0 to 100 with higher scores indicating better health. Domain scores are calculated from raw scores such that domain scores have a mean of 50 and SD of 10. The PCS and MCS summary component scores also have mean of 50 and SD of 10 to allow comparisons with domain scores.

Scoring the SF-12 version 2 is accomplished using T-score Based scoring software from QualityMetric Inc. (Lincoln, RI). T-score Based scoring is standardized across the SF family of adult tools using the means and standard deviations from the 2009 U.S. general population. The T-score Based scores in the U.S. general population have a mean of 50 and a standard deviation of 10. The Medical Outcomes Study (MOS) tools utilize 2009 t-scores.

The main advantage of T-score Based scoring of the adult SF tools is easier interpretation. By using the T-score Based scoring method, your data are scored in relation to U.S. general population t-scores. Therefore, all scores obtained that are below 50 can be interpreted as below the U.S. general population t-score and scores above 50 can be interpreted as above the U.S. general population t-score. Because the standard deviation for each scale is 10, it is easier to see exactly how far above or below the mean a score is in standard deviation units (10 points = 1 standard deviation unit).

5.8.8 Pediatric Evaluation of Disability Inventory Computer Adaptive Test (PEDI-CAT)

The Pediatric Evaluation of Disability Inventory Computer Adaptive Test (PEDI-CAT) is a measure of functional capabilities and performance designed for use in children and youth from birth through 20 years of age with a variety of physical conditions (Haley et al. 2011). PEDI-CAT includes 4 domains (daily activities, mobility, social/cognitive and responsibility). Only 3 domain scores (daily activities, mobility, social/cognitive) will be included in the analysis for the subjects under 3 years of old. Each of the 4 PEDI CAT domains will be presented as Score, SE, T-Score and Percentile. Higher is better for Score, T-Score and Percentile. The assessment will be administered at select sites.

5.8.9 Gait, using gait analysis by computerized mat during the 6MWT

At select sites, the computerized mat may be used to assess gait during the 6MWT as the subject walks across the mat. The following gait assessments will be assessed at select sites:

- Stride Length (cm)
- Base of Support (cm)
- Double Support (% of gait cycle)
- Velocity (cm/sec)
- Cadence (steps/minute)

5.8.10 Beery-Buktenica Developmental Test of Visual Motor Integration (Beery-VMI)

The Beery-VMI measures the extent to which individuals can integrate their visual and motor abilities (Beery et al. 2004). The test is normed for children 2-18 years of age. The Beery-VMI will be administered to subjects at select sites to obtain the following scores: Raw Score (Range 0–30, higher is better), Standard Score, Scaled Score, and Percentile.

5.8.11 Raven's Coloured Progressive Matrices (RCPM)

The RCPM is a test of spatial understanding and abstract reasoning developed for individuals 5 years of age and older (Raven et al. 1998). At select sites, the RCPM will be administered to all subjects, at the clinical judgment of the test administrator, to obtain Total Score (Range 0–60, higher is better) and Percentile.

6 ANALYSIS POPULATIONS

The following analysis sets are defined for this study.

6.1 Screened Population

The Screened Population will consist of all subjects who underwent a Screening Visit.

6.2 Randomized Population

The Randomized Population will consist of all subjects in the Screened Population who were randomized to a treatment group in the study.

6.3 Efficacy Analysis Set

The Efficacy Analysis Set includes all randomized subjects who received at least one dose of investigational product. For efficacy analyses, subjects are analyzed according to study treatment as randomized.

6.3.1 Efficacy Analysis Set – Observable Seizures

The Efficacy Analysis Set – Observable Seizures is the subset of subjects in the Efficacy Analysis Set who are Observable Seizures Subjects (see Section 5.6).

6.3.2 Efficacy Analysis Set – Absence Seizures

The Efficacy Analysis Set – Absence Seizures is the subset of subjects in the Efficacy Analysis Set who are Absence Seizures Subjects (see Section 5.6).

6.3.3 Efficacy Analysis Set – Observable Seizures Only

The Efficacy Analysis Set – Observable Seizures Only is the subset of subjects in the Efficacy Analysis Set who are Observable Seizures Only Subjects (see Section 5.6).

6.3.4 Efficacy Analysis Set – Absence Seizures Only

The Efficacy Analysis Set – Absence Seizures Only is the subset of subjects in the Efficacy Analysis Set who are Absence Seizures Only Subjects (includes some subjects with fewer than 4 observable seizures per 4 weeks, see Section 5.6).

6.3.5 Efficacy Analysis Set – CANTAB

The efficacy analysis set – CANTAB is the subset of subjects in the efficacy analysis set who had a baseline and at least one post baseline (Week 4 or Week 8) CANTAB assessment performed.

6.3.6 Efficacy Analysis Set – 6MWT

The efficacy analysis set – 6MWT is the subset of subjects in the efficacy analysis set who had a baseline and at least one post baseline (Week 4 or Week 8) 6MWT assessment performed.

6.3.7 Efficacy Analysis Set – GMFM-88

The efficacy analysis set – GMFM-88 is the subset of subjects in the efficacy analysis set who had a baseline and at least one post baseline (Week 4 or Week 8) GMFM-88 assessment performed.

6.3.8 Efficacy Analysis Set – CNS

The efficacy analysis set – CNS is the subset of subjects in the efficacy analysis set who had a baseline and Week 8 CNS assessment performed.

6.3.9 Efficacy Analysis Set – CGI-I

The efficacy analysis set – CGI-I is the subset of subjects in the efficacy analysis set who had CGI-I assessment performed at Week 8.

6.3.10 Efficacy Analysis Set – SF-10

The efficacy analysis set – SF-10 is the subset of subjects in the efficacy analysis set who had a baseline and Week 8 SF-10 assessment performed.

6.3.11 Efficacy Analysis Set – SF-12

The efficacy analysis set – SF-12 is the subset of subjects in the efficacy analysis set who had a baseline and Week 8 SF-12 assessment performed.

6.4 Per Protocol Analysis Set

The Per Protocol Analysis Set is the subset of subjects in the Efficacy Analysis Set who also meet the following criteria:

- met all inclusion and exclusion criteria at the time of randomization
- have $\geq 80\%$ dosing compliance from baseline to week 8
- have sufficiently complete seizure data
 - Observable Seizures Subjects: completed at least 28 days of the seizure diary during the 6-week baseline period and again during weeks 3-8 of the double-blind placebo-controlled treatment period

- Absence Seizures Only Subjects: at least 8 hours evaluable EEG at randomization and again at week 8

6.4.1 Per Protocol Analysis Set – Observable Seizures

The Per Protocol Analysis Set – Observable Seizures is the subset of subjects in the Efficacy Analysis Set – Observable Seizures who met the following criteria:

- met all inclusion and exclusion criteria at the time of randomization
- have $\geq 80\%$ dosing compliance from baseline to week 8
- have sufficiently complete seizure data: completed at least 28 days of the seizure diary during the 6-week baseline period and again during weeks 3-8 of the double-blind placebo-controlled treatment period

6.4.2 Per Protocol Analysis Set – Absence Seizures

The Per Protocol Analysis Set – Absence Seizures is the subset of subjects in the Efficacy Analysis Set – Absence Seizures who met the following criteria:

- met all inclusion and exclusion criteria at the time of randomization
- have $\geq 80\%$ dosing compliance from baseline to week 8
- have sufficiently complete seizure data: at least 8 hours evaluable EEG at randomization and again at week 8

6.4.3 Per Protocol Analysis Set – CANTAB

The Efficacy Analysis Set – CANTAB is the subset of subjects in the Efficacy Analysis Set – CANTAB who met all inclusion and exclusion criteria at the time of randomization and have $\geq 80\%$ dosing compliance from baseline to week 8.

6.5 Safety Analysis Set

The Safety Analysis Set includes all subjects who receive at least one dose of investigational product. For safety analyses during the double-blind period, subjects are summarized according to first study treatment actually received: either UX007 or placebo. Separate listings will capture actual dosing throughout.

6.6 Extension Analysis Set

The Extension Analysis Set is the subset of subjects in the Safety Analysis Set who continued after the 8 week double-blind placebo-controlled treatment period into the open-label extension period.

6.7 Pharmacokinetics Analysis Set

The Pharmacokinetics Analysis Set (PK Analysis Set) includes all subjects with available PK data.

7 DATA HANDLING AND ACCEPTANCE

7.1 Handling of Missing and Incomplete Data

Missing clinical outcome data can occur for multiple reasons, including missed subject visits and scales or measures with missing item scores. Missing and incomplete data will be identified through a review of tables and listings for this study. Missing and incomplete data will be identified for investigation and possible resolution by Data Management prior to the study database lock.

Unless otherwise specified, for missing assessments for an individual subject, these data would remain as missing. When a change from baseline is assessed, only subjects with a baseline and at least one post baseline measurement will be included in the analysis.

For primary and secondary analyses related to reduction in seizures from baseline to Week 8, imputation will be used to enable inclusion in analyses of all subjects in the Efficacy Analysis Set, the Efficacy Analysis Set – Observable Seizures and the Efficacy Analysis Set – Absence Seizures.

- For observable seizures subjects who have incomplete diary data during the Baseline Period but at least one day complete, observable seizure frequency will be calculated by averaging over the days with complete diary data. The same rule will be used for the Double-Blind Placebo-Controlled Treatment Period. Note that this also applies to subjects who terminate early.
- For absence seizures subjects who have incomplete EEG at either Randomization or Week 8, absence seizure frequency will be calculated by averaging over the time that is complete, even if the EEG is not done overnight.
- For subjects who have completely missing data for either Randomization or Week 8, a reduction from baseline in the natural logarithm of seizure frequency (+ 1) value of zero will be imputed for the response variable in any analyses of reduction from baseline, and non-response will be imputed for the response variable in any analyses of seizure response. For subjects who have completely missing data for Randomization, the Week 8 value will be imputed if available for the baseline covariate; if both Randomization and Week 8 are missing then the average baseline value of the subjects with complete data in the same treatment group will be imputed for the baseline covariate. In additional analyses related to reduction in seizures, two alternate methods will be implemented:
 - the average reduction from baseline in the logarithm of seizure frequency (+ 1) of the subjects with complete data in the same treatment group will be imputed for the response variable in any analyses of reduction from baseline; and response will be imputed as yes if the imputed reduction from baseline is greater than or equal to the natural logarithm of 2 and no otherwise in any analyses of seizure response
 - no imputation, or complete case analysis – these data would remain as missing.

Imputation will not be used for analyses involving the open label period.

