3.3 Blinding and Randomization Methods

Eligible subjects will be enrolled in the study and sequentially assigned an identification number. Subjects will be assigned to investigational product or placebo treatment groups via manual randomization based on a manual randomization process developed by the Sponsor. Randomization will seek to stratify subjects based on seizure frequency reported during the 6-week baseline period. At the end of the Baseline Period, eligible subjects will be randomized in a 3:1 ratio to either UX007 or placebo. Note that the first 3 subjects PPD [REDACTED] were randomized in a 1:1 ratio because they were randomized prior to the implementation of Protocol Amendment 3.

The titration and Treatment Period (Weeks 0-8) will be conducted as a randomized, double-blind, placebo-controlled study. Double-blind conditions will be established so that neither the sponsor, subject or site personnel involved in study conduct will know the identity of a subject's treatment. Following completion of the double-blind period, all eligible subjects will receive open-label UX007 for a 44-week open-label Extension Period (Weeks 9-52) to assess long-term safety and duration of effect.

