3.5 Sample Size Considerations

The proposed Phase 2 study will have a sample size that would likely detect a 50% reduction from baseline in seizure frequency compared to placebo. Such a treatment effect would be greater than or equal to that demonstrated by many of the approved AEDs for refractory epilepsy, such as lamotrigine, oxcarbazepine and levetiracetam ([Glauser et al. 2000](#)), ([Glauser et al. 2006](#)), ([Trevathan et al. 2006](#)). A theoretical treatment effect of this magnitude, in light of the benign safety profile of UX007 shown to date, is considered to be clinically meaningful by physician experts. From the perspective of accurately determining seizure frequency, the proposed durations are deemed sufficient and are accounted for in the standard deviation (55%) used in the power calculation.

For the study to be adequately powered, a sample of approximately 40 completed subjects was estimated to be adequate to detect a 50% between-group difference in seizure frequency per 4 weeks with power of approximately 80% and population standard deviation of 55% using two-sample t test at one-sided alpha level of 0.05.

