8 STATISTICAL METHODS OF ANALYSIS

8.1 General Principles

During the Double-Blind Placebo-Controlled Treatment Period, efficacy analyses will be based on the Efficacy Analysis Set or the Per Protocol Analysis Set. During the open label period, efficacy analyses will be based on the Extension Set. Safety analyses will be based on the Safety Analysis Set. Unless stated otherwise, statistical tests will be 1-sided hypothesis tests performed at the 5% level of significance and confidence intervals will be 2-sided 90% confidence intervals. Continuous variables will be summarized by number of subjects and mean, standard deviation (SD), median, minimum, and maximum values. Categorical variables will be summarized by number and percentage of subjects.

Analyses and summaries by study period will be done for the following time periods:

- Double-blind placebo-controlled treatment period: after the date of the randomization visit until the date of the week 8 visit
- Open-label extension period: after the date of the week 8 visit until the date of the week 52 visit
- Dose exploration period: after the date of the week 26 visit until the date of the week 36 visit

Overall analyses and summaries will include all subjects and ignore treatment assignment.

For logarithmic transformations of seizure frequency, the natural logarithm will be used and a value of 1 will be added prior to performing the transformation.

For analyses and summaries of subjects while taking UX007, the time while taking placebo will be excluded and the original baseline will be used for all subjects regardless of which treatment was taken during the double-blind placebo-controlled treatment period.

Graphical displays of select study endpoints will be completed and include both observed study data and modeled analyses. Arithmetic means, least square means (LSM), and appropriate measure of dispersion (e.g., standard deviation, standard error) or confidence intervals may be displayed in figures.

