8.6.3 Primary Efficacy Endpoint

The primary efficacy endpoint is the reduction from baseline to week 8 in frequency of seizures (normalized to a 4-week rate): observable seizures measured for 6 weeks after 2-week titration by diary and absence seizures measured overnight by electroencephalography (EEG). Observable seizure frequency at baseline will be calculated based on approximately 6 weeks between the screening and randomization visits and observable seizure frequency at week 8 will be calculated based on approximately 6 weeks between the end of titration and the week 8 visit (see Section 5.7.1). Absence seizure frequency will be based on overnight EEG at the randomization and week 8 visits.

The primary efficacy endpoint will be derived for each subject based on subject seizure type at randomization: observable seizures from the diary will be used for Observable Seizures Subjects and absence seizures from EEG will be used for Absence Seizures Only Subjects (see Section 5.6).

The primary efficacy endpoint will be analyzed, based on the Efficacy Analysis Set, using a linear regression (ANCOVA) model as described for continuous endpoints in Section 8.6.1. Logarithmic transformations will be used for modeling. The response variable in the model will be the reduction in the natural logarithm of the seizure frequency (+ 1) from baseline to Week 8 and the baseline covariate will be the natural logarithm of the baseline seizure frequency (+ 1): observable seizures from the diary will be used for Observable Seizures Subjects and absence seizures from EEG will be used for Absence Seizures Only Subjects.

An additional covariate will be included that indicates whether the subject is an Observable Seizures Subject or an Absence Seizures Only Subject. Estimates and 90% confidence intervals of percent reduction in seizure frequency will be derived from the model for each treatment group and for the difference between groups.

Missing data will be imputed as specified in Section 7.1. Sensitivity analysis assessing the impact of missing data will be performed using the methods described in Section 7.1.

Percent reduction from baseline in frequency of seizures over the entire study period will be summarized by visit (see Section 5.7.1), and by treatment group, for subjects while taking UX007, and overall.

The following additional analyses will be performed:

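### The alternate imputation method for missing seizure data enters each arm's own mean as if observed, so this sensitivity analysis understates its standard error

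*SAP*

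**What the plan says.** SAP Section 7.1 gives a main rule for subjects whose seizure data are completely missing at Randomization or Week 8: zero reduction in the log of frequency plus one, and non-response. It then names two alternates. Under the first, the average log reduction "of the subjects with complete data in the same treatment group will be imputed" as the response when reduction is analysed; seizure response is then set to yes if that imputed value reaches the natural logarithm of 2, and to no otherwise. The second alternate is complete case.

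Section 8.6.3 gives these methods their role for the primary endpoint: "Sensitivity analysis assessing the impact of missing data will be performed using the methods described in Section 7.1". The primary endpoint is analysed "using a linear regression (ANCOVA) model as described for continuous endpoints in Section 8.6.1". Section 8.6.4 runs the alternates for the secondary seizure endpoints as well, and Table 6 lists ANCOVA and logistic tables for the alternate imputation method and, separately, for complete case.

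Nothing in the text mentions multiple imputation, added residual variation or an adjusted standard error. The Appendix D code is blacked out, so a correction there cannot be excluded, but the appendix is titled as code for the primary analysis.

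**The concern.** An arm-mean fill-in contributes almost no residual but counts as a full subject in the sample size and degrees of freedom. The fitted treatment difference stays essentially where complete case puts it, while the standard error falls. The table would then show the complete-case estimate with a narrower interval and a more extreme test statistic. It would test no missing-data assumption that complete case does not already make, yet it could be read as independent support for the result.

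The response endpoints have a different problem. One yes or no, decided by whether the arm mean reaches ln 2, is given to every imputed subject in the arm. That can move the estimated difference itself, in either direction.

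**Working it through.** **Inputs.** Level, from SAP Section 8.1: "statistical tests will be 1-sided hypothesis tests performed at the 5% level of significance", with two-sided 90% intervals. Sample size, from Section 3.5: "a sample of approximately 40 completed subjects was estimated to be adequate to detect a 50% between-group difference", "with power of approximately 80% and population standard deviation of 55% using two-sample t test at one-sided alpha level of 0.05". Allocation, from Section 3.3: "eligible subjects will be randomized in a 3:1 ratio to either UX007 or placebo". I take 30 UX007 and 10 placebo, ignoring that the first three subjects were randomized 1:1. No missing rate is stated, so one subject to 30% is assumed.

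**The plan's own figure.** SE = 55 × √(1/30 + 1/10) = 20.1; 50/20.1 = 2.49; 2.49 − 1.645 = 0.845, giving power of 80.1%. The exact noncentral t gives 78.8%. The stated value of about 80% is reproduced at 30:10.

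**Formula for the continuous endpoints (two-sample t).** Let N, n1, n0 be the randomized totals and R, r1, r0 the observed ones. The estimated difference is unchanged by the fill-in, and

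SE ratio (imputed to complete case) = √[ (R−2)/(N−2) × (1/n1 + 1/n0)/(1/r1 + 1/r0) ]

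True one-sided size = P( t with R−2 df > t(0.95, N−2) × SE ratio )

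Coverage of the 90% interval = 1 − 2 × size.

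No standard deviation is needed. Example, 27:9 observed: (34/38) × (0.1333/0.1481) = 0.805, square root 0.897; 1.686 × 0.897 = 1.51; P(t34 > 1.51) = 7.0%.

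| Missing, UX007 + placebo | Share | SE ratio | True size | 90% CI coverage | Simulated size |
|---|---|---|---|---|---|
| 1 + 0 | 2.5% | 0.983 | 5.3% | 89.4% | not run |
| 0 + 1 | 2.5% | 0.948 | 5.9% | 88.2% | not run |
| 1 + 1 | 5% | 0.931 | 6.3% | 87.5% | 6.1% |
| 4 + 0 | 10% | 0.928 | 6.3% | 87.3% | 6.0% |
| 3 + 1 | 10% | 0.897 | 7.0% | 86.0% | 7.0% |
| 6 + 2 | 20% | 0.795 | 9.5% | 81.0% | 9.2% |
| 9 + 3 | 30% | 0.692 | 12.7% | 74.6% | 12.6% |

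The last column comes from 40,000 null trials per setting, using ANCOVA with a baseline covariate and a seizure-type indicator and data missing completely at random. Residual SD 0.9, baseline slope 0.3 and 35% absence-only subjects are assumed. In the same trials complete case held 4.8% to 5.1% and zero imputation 4.6% to 5.1%. At 20% missing, the mean model SE under arm-mean imputation was 0.301 against a true SD of the estimate of 0.378; for complete case it was 0.377 against 0.381.

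**Response endpoints (illustrative counts).** Suppose 13/27 UX007 and 2/9 placebo completers respond, with 3 and 1 missing. Complete case gives 48.1% − 22.2% = 25.9 points. After imputation:

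- Both arm means below ln 2: 13/30 − 2/10 = 23.3 points.
- Both at or above ln 2: 16/30 − 3/10 = 23.3 points.
- Only UX007 at or above ln 2: 16/30 − 2/10 = 33.3 points.
- Only placebo at or above ln 2: 13/30 − 3/10 = 13.3 points.

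**The case against.** The strongest reply is that nothing is decided on this analysis. The primary test uses zero imputation, the fallback procedure in Section 8.6.3 does not call on the alternates, and the complete-case tables in Table 6 put the same estimate next to a valid interval. That stands, and it confines the point to a reporting fault in a sensitivity analysis. A reader might infer that the trial's false-positive rate is raised; the documents do not support that.

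A reader might also infer that this method always looks more favourable to UX007 than complete case. It does not. For the response endpoints the difference can shrink, as shown above. For the continuous endpoints a small standard error magnifies the statistic in whichever direction the estimate points, so an unfavourable result would look worse.

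The number imputed may also be small. One complete diary day, or a partial EEG, is enough to avoid imputation, and the diary rule covers early terminators. The 9.5% figure needs eight of 40 subjects with no usable data, so it should not be read as expected. This reply is weaker for EEG. Overnight EEG is not scheduled at the Week 52/early termination visit, so a subject who leaves before Week 8 may have no post-baseline EEG. EEG supplies the primary endpoint for Absence Seizures Only Subjects and all the absence-seizure secondaries.

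**Conclusion.** The point holds for the first alternate method only. As written, the rule gives the continuous seizure endpoints a standard error that is too small at essentially the complete-case estimate. It gives the response endpoints a common arm-level yes or no that can distort the difference either way. The size depends on a missing rate that the documents do not state. At 30:10 the true one-sided size runs from 5.3% with one UX007 subject missing to 9.5% at 20% missing. These figures assume data missing completely at random and no variance correction in the blacked-out code. The primary analysis and complete case are untouched. The change is worth making because SAP version 2.0 added missing-data sensitivity analyses to the primary section, and one of the two alternates there does not test robustness.

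**What to change.** The simplest change is to delete the arm-mean rule from SAP Section 7.1 and the corresponding Table 6 entries, since complete case already gives that estimate with a valid interval.

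If a second method is wanted, replace the rule with multiple imputation combined by Rubin's rules:

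- Use one simple imputation model pooled across arms with a treatment term, because about 10 placebo subjects are too few for a separate model.
- Derive response from each imputed Week 8 frequency, not from an arm mean.
- Add a delta-adjusted or placebo-based version. Multiple imputation that uses only the ANCOVA covariates would nearly reproduce complete case and test nothing new.

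Keep complete case in either event. Deletion costs only SAP wording. Replacement costs a little more programming in standard SAS procedures and a wider interval in this table. Neither changes data collection or trial conduct.
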